# SPONSOR PERSONNEL ORA PERSONNEL

# MEDICAL MONITOR

# **SYNOPSIS**

[figure not shown]
Protocol Title:	A Multi-Center, Phase 2b, Randomized, Double-Masked, Parallel-Group, Vehicle- Controlled, Clinical Study to Assess the Safety and Efficacy of Reproxalap Ophthalmic Solution (0.25% and 0.1%) Compared to Vehicle in Subjects with Dry Eye Disease
Protocol Number:	ADX-102-DED-009
	1) Reproxalap Ophthalmic Solution (0.25%)
Investigational Product:	2) Reproxalap Ophthalmic Solution (0.1%)
	3) Vehicle Ophthalmic Solution
Study Phase:	2b
Objective(s):	To evaluate the efficacy of Reproxalap Ophthalmic Solutions (0.25% and 0.1%) on baseline to weeks 2, 4, 8 and 12 change score  To evaluate effect sizes for efficacy endpoints of Reproxalap Ophthalmic Solutions (0.25% and 0.1%) vs vehicle for the treatment of the signs and symptoms of dry eye disease to confirm the endpoint selection and sample size for Phase 3 studies with ADX-102.  To evaluate the safety and tolerability of Reproxalap Ophthalmic Solutions (0.25% and 0.1%) to vehicle
Overall Study Design:	
Structure:	Multi-center, double-masked, randomized study
Duration:	An individual subject's participation is estimated to be approximately 14 weeks (98 days).
Controls:	Vehicle Ophthalmic Solution
Dosage/Dose Regimen/ Instillation/Application/Use:	Screening: Between Visits 1 and 2, all subjects will receive 14 consecutive days (± 2) of Run-in (vehicle) ocular drops self–administered QID in both eyes.

	Treatment: During the 12 week ( $84 \pm 3$ days) treatment period, Reproxalap Ophthalmic Solution at concentrations of 0.1%, 0.25% or vehicle ophthalmic solution will be administered QID by bilateral topical ocular dosing. Subjects will be randomized to one of three treatment groups (1:1:1) to receive study drug after the Post–CAE® assessments at Visit 2.			
Summary of Visit Schedule:	
 
6 visits over the course of approximately 14 weeks
 
Visit 1 = Day -14 ± 2, CAE® Screening
 
Visit 2 = Day 1, CAE® Confirmation/ Baseline
 
Visit 3 = Day 15 ± 2, 2-Week Follow-Up
 
Visit 4 = Day 29 ± 2, 4-Week Follow-Up
 
Visit 5 = Day 57 ± 3, 8-Week Follow-Up
 
Visit 6 = Day 85 ± 3, 12-Week CAE® Follow-Up
 
& Study Exit
 
			
Measures Taken to Reduce Bias:	This is a randomized treatment assignment, double-masked study.			
Study Population Characteristics:				
Number of Subjects:	Approximately 750 subjects will be screened to enroll approximately 300 subjects (100 per treatment group).			
Condition/Disease:	Dry Eye Disease (DED)			

### Subjects must:

- 1. Be at least 18 years of age of either gender and any race;
- Provide written informed consent and sign the Health Information Portability and Accountability Act (HIPAA) form;
- 3. Have a reported history of dry eye for at least 6 months prior to Visit 1;
- Have a history of use or desire to use eye drops for dry eye symptoms within 6 months of Visit 1;
- 5.
- 6. Have a Schirmer's Test score of ≤ 10 mm and ≥ 1 mm at Visit 1 and Visit 2;
- 7.
- 8. Have a corneal fluorescein staining score in at least one region (e.g. inferior, superior, or central) at Visit 1 and Visit 2 Pre-CAE®;
- 9.
- 11. Demonstrate a response to the CAE® at Visits 1 and 2 as defined by:
  - A. Having at least a increase in fluorescein staining in the inferior region in at least one eye following CAE® exposure;
  - B. Reporting an Ocular Discomfort score

**Inclusion Criteria:** 

- plugs during the study that have not been stable within 30 days of Visit 1;
- 9. Be currently taking any topical ophthalmic prescription (including medications for glaucoma) or over-the-counter (OTC) solutions, artificial tears, gels or scrubs, and cannot discontinue these medications for the duration of the trial (excluding medications allowed for the conduct of the study);
- 10. Have corrected visual acuity greater than or equal to logarithm of the minimum angle of resolution (logMAR) + 0.7 as assessed by Early Treatment of Diabetic Retinopathy Study (ETDRS) scale in both eyes at Visit 1;
- 11. Be a woman who is pregnant, nursing, or planning a pregnancy;
- 12. Be unwilling to submit a urine pregnancy test at Visit 1 and Visit 6 (or early termination visit) if of childbearing potential. Non-childbearing potential is defined as a woman who is permanently sterilized (e.g., has had a hysterectomy or tubal ligation), or is postmenopausal (without menses for 12 consecutive months);
- 13. Be a man or woman of childbearing potential who is not using an acceptable means of birth control; acceptable methods of contraception include: hormonal oral, implantable, injectable, or transdermal contraceptives; mechanical spermicide in conjunction with a barrier such as a diaphragm or condom; intrauterine device (IUD); or surgical sterilization of partner. For non-sexually active males or females, abstinence may be regarded as an adequate method of birth control; however, if the subject becomes sexually active during the study, he/she must agree to use adequate birth control as defined above for the remainder of the study;
- 14. Have a known allergy and/or sensitivity to the

	The state of the s
	test article or its components;
	15. Have a condition or be in a situation which the investigator feels may put the subject at significant risk, may confound the study results, or may interfere significantly with the subject's participation in the study;
	16. Be currently enrolled in an investigational drug or device study or have used an investigational drug or device within 30 days of Visit 1;
	17. Have previously used reproxalap ophthalmic solution;
	18.
	
 
Be unable or unwilling to follow instructions, including participation in all study assessments and visits.
 

Carlo Francisco de la constante de la constant	0.25% Reproxalap Ophthalmic Solution
Study Formulations and Formulation Numbers:	0.1% Reproxalap Ophthalmic Solution
	Vehicle Ophthalmic Solution
Evaluation Criteria:	
Efficacy Measures and Endpoints:	Ora Calibra ® Ocular Discomfort &     4-Symptom Questionnaire

Safety Measures:	
 
Visual acuity
 
Slit-lamp evaluation
 
Adverse event query
 
Intraocular Pressure (IOP)
 
Dilated fundoscopy
 

# General Statistical Methods and Types of Analyses

Sample Size

# Efficacy Analysis

Evaluate baseline to weeks 2, 4, 8 and 12 change scores with reproxalap on DED

Summary of Known and Potential Risks and Benefits to Human Subjects Refer to Investigator's Brochure.

# LIST OF ABBREVIATIONS

AE adverse event			
API	active pharmaceutical ingredient		
BCVA	best-corrected visual acuity		
CAE	controlled adverse environment		
CFR	Code of Federal Regulations		
CI	confidence interval		
C max	maximum concentration		
CPT	Current Procedural Terminology		
CRA	clinical research associate		
CRF	case report form		
CRO	contract research organization		
CV	coefficient of variation		
DED	dry eye disease		
DHHS	Department of Health and Human Services		
eCRF	electronic case report form		
ETDRS	Early Treatment Diabetic Retinopathy Study		
FDA	Food and Drug Administration		
GCP	Good Clinical Practice		
GLP	Good Laboratory Practice		
GMP	Good Manufacturing Practice		
HIPAA	Health Insurance Portability and Accountability Act		
IB	Investigator's brochure		
ICF	informed consent form		
ICH	International Conference on Harmonisation		
IEC	Independent Ethics Committee		
IM	intramuscular		
IND	investigational new drug application		
IOP intraocular pressure			
IP	investigational product		
IRB	institutional review board		
ITT	intent to treat		
KCS	keratoconjunctivitis sicca		
LASIK	laser in situ keratomileusis		
LOCF	last observation carried forward		
logMAR	logarithm of the minimum angle of resolution		
MedDRA Medical Dictionary for Regulatory Activities			
NCS	not clinically significant		

[figure not shown]
ND	not done		
NDA	new drug application		
NF	national formulary		
NSAID	nonsteroidal anti-inflammatory drug		
OD	right eye		
OS	left eye		
OU	both eyes		
OTC	over the counter		
PE	polyethylene		
PHI	protected health information		
PO	by mouth		
PP	per protocol		
PRN	as needed		
QD	once daily		
QID	Four times daily		
QS	as much as will suffice		
ROPI	Report of Prior Investigations		
SAE	serious adverse event		
SAP	statistical analysis plan		
SD	standard deviation		
SOP	standard operating procedure		
TF	tear film		
$T_{\text{max}}$	time of maximum concentration		
USP	United States Pharmacopeia		
VA	visual acuity		
w/v	weight per unit volume		

[figure not shown]
# 1 INTRODUCTION

# 2 Clinical Studies of Reproxalap Ophthalmic Solution

[figure not shown]
NA = not applicable; QID = 4-times daily

Table 2. Topical Ocular Reproxalap Clinical Trial Outcomes

Clinical Trial	Indication	Summary Outcome
-		

### 3 STUDY OBJECTIVES

The study objectives are as stated below:

- To evaluate the efficacy of Reproxalap Ophthalmic Solutions (0.25% and 0.1%) on baseline to weeks 2, 4, 8 and 12 change scores
- To evaluate effect sizes for efficacy endpoints of Reproxalap Ophthalmic Solutions (0.25% and 0.1%) versus vehicle for the treatment of the signs and symptoms of dry eye disease to confirm the endpoint selection and sample size for Phase 3 studies with ADX-102.
- To evaluate the safety and tolerability of Reproxalap Ophthalmic Solutions (0.25% and 0.1%) to vehicle

### 4 CLINICAL HYPOTHESES

The clinical hypotheses for this study are that 0.10% and/or 0.25% Reproxalap Ophthalmic Solution is superior to vehicle

### 5 OVERALL STUDY DESIGN

This is a Phase 2b, multicenter, randomized, double—masked, vehicle-controlled, parallel-group design with block enrollment. Subjects will be randomized to one of the following treatment groups at Visit 2 and will be instructed to follow a QID-dosing regimen:

[figure not shown]
- Reproxalap 0.1% Ophthalmic Solution (N~100)
- Reproxalap 0.25% Ophthalmic Solution (N~100)
- Vehicle of Reproxalap Ophthalmic Solution (N~100)

[figure not shown]
This study is multicenter, randomized, double—masked, vehicle—controlled, parallel-group design with block enrollment. Approximately 300 subjects will be randomly assigned to one of the three treatment groups (1:1:1) to receive either Reproxalap Ophthalmic Solution (0.1%, 0.25%) or vehicle solution as topical ophthalmic drops administered bilaterally QID. Subjects, Sponsor, CRO and site personnel will be masked to treatment assignment.

During the screening period, two 90-minute exposures to the CAE® will be conducted to ascertain eligibility to enter the study. Those who qualify will be randomized to receive study drug in a double-masked fashion for 84 days. Subjects will self-administer drops four times daily and will complete daily diary assessments as instructed.

At Visit 6 (Day 85), CAE® exposure will occur, with pre-CAE®, during CAE® (symptoms only) and post-CAE® assessments of ocular signs and symptoms. At Visits 3, 4 and 5, no CAE® exposure will occur

The total number of expected participants, including screen failures, is approximately 750 subjects.

Subjects who terminate early during the treatment period will be asked to complete safety assessments prior to commencement of any alternative dry eye therapy (if at all possible). Subjects who are terminated early from the study will not be replaced.

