### 7 STUDY PARAMETERS

### 7.1 Efficacy Measures and Endpoints

### 7.1.1 Efficacy Measure(s)

### 7.1.2 Efficacy Endpoint(s)

The efficacy endpoints are changes from baseline at weeks 2, 4, 8 and 12 for each efficacy measure, where available. Endpoints will be calculated pre-CAE and, where available post-CAE and as pre- to post-CAE changes.

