#### 11.4.2 Unit of Analysis

Safety endpoints will be analyzed for both eyes. For efficacy endpoints, the unit of analysis will be the study eye, or the "worst eye," as defined by the following:

Analyses will be performed on the ITT population with the Last Observation Carried Forward (LOCF) imputation method for missing values. Efficacy analyses may also be conducted using the ITT population with observed data only (i.e., without LOCF) and the PP population to assess sensitivity as detailed further in the statistical analysis plan (SAP).

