13.6.1 ASSESSMENTS DURING VISITS

Pre-CAE[®], post-CAE[®], change from pre-CAE[®] to post-CAE[®] and changes from baseline in ocular discomfort and dry eye symptoms will be analyzed

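### CAE endpoints have no on-treatment value before Visit 6, so for early leavers LOCF means either an untreated Visit 2 score or a completers' analysis

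*Protocol*

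**What the plan says.** **Schedule.** Protocol section 5 places "two 90-minute exposures to the CAE® will be conducted to ascertain eligibility to enter the study" in the screening period. The Synopsis has subjects randomised "to receive study drug after the Post–CAE® assessments at Visit 2", so both exposures precede study drug. Section 5 continues: "At Visit 6 (Day 85), CAE® exposure will occur, with pre-CAE®, during CAE® (symptoms only) and post-CAE® assessments of ocular signs and symptoms". For the visits in between: "At Visits 3, 4 and 5, no CAE® exposure will occur".

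**Endpoints.** Protocol 7.1.2 defines changes from baseline at weeks 2, 4, 8 and 12 and adds: "Endpoints will be calculated pre-CAE and, where available post-CAE and as pre- to post-CAE changes". SAP 13.6.1 likewise lists "change from pre-CAE" to post-CAE among the symptom analyses. Protocol 7.1.3 sets success at week 12, on any one sign or symptom.

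**Missing data.** ITT is everyone randomised (Protocol 11.1). The text under 11.4.2 (the contents list numbers Missing Data as 11.4.3) says: "Analyses will be performed on the ITT population with the Last Observation Carried Forward (LOCF) imputation method for missing values". It adds: "Efficacy analyses may also be conducted using the ITT population with observed data only". The visible wording neither limits LOCF to post-baseline values nor treats CAE measures separately. SAP section 1 says its methods supersede the protocol's, but the content of SAP 8.2 (missing data) and 8.3 (baseline) is not visible. The efficacy tables in SAP section 20 are labelled either ITT with LOCF or ITT with observed data only.

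**Early leavers.** Protocol section 5 asks them for safety assessments and does not replace them. An early termination visit is mentioned in the exclusion criteria, but its full content is not visible.

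**The concern.** LOCF is usually questioned because the carried value is old. Here the difficulty comes earlier. A measure taken at weeks 2, 4 and 8 has an on-treatment value to carry for any subject who reached one of those visits. A post-CAE score, a during-CAE symptom score or a pre- to post-CAE change has none before Visit 6, whatever the carry-forward rule says. The label "ITT with LOCF" must then mean something different for CAE endpoints than for the rest.

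What is at stake is the comparison between endpoints. One stated objective is to obtain effect sizes that confirm endpoint selection and sample size for Phase 3. If early leavers are scored as zero change on CAE endpoints only, those effect sizes are pulled toward zero and depend on how dropout differs between arms. If early leavers are left out, the CAE results describe completers while the non-CAE results largely describe everyone randomised.

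**Working it through.** **1. CAE exposures by visit (Protocol section 5 and Synopsis)**

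| Visit | Study drug taken before the exposure | CAE run |
|---|---|---|
| 1 (Day -14) | no | yes |
| 2 (Day 1) | no | yes |
| 3, 4, 5 (Days 15, 29, 57) | yes | no |
| 6 (Day 85) | yes | yes |

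On-treatment CAE values before Visit 6: none.

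**2. What LOCF does for a subject who leaves before Visit 6**

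- *Baseline carried:* week 12 value = Visit 2 value, so change = 0 exactly.
- *Post-baseline only:* nothing to carry. The subject drops out of the endpoint, and the LOCF and observed-data results coincide.

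**3. Size**

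The plan's 100 per group cannot be rebuilt, because no effect size, SD, power or dropout rate is visible. All of the following are assumptions: 100 per arm, SD of change 1, vehicle improvement mV = 0.5 SD, true effect δ = 0.40 SD, dropout dA (active) and dV (vehicle) from 5% to 20% and unrelated to outcome, two-sided t-test at 0.05. Equal dropout of 5%, 10% or 20% in all arms leaves 15, 30 or 60 of 300 subjects without a Visit 6 CAE value. With complete data, SE = √(2/100) = 0.141 and power is 80%.

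Baseline carried:

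- difference = (1−dA)(mV+δ) − (1−dV)mV
- variance per subject in an arm with completer mean m = (1−d) + d(1−d)m²
- SE = √[(vA + vV)/100]

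Worked case, 10% in both arms: difference = 0.9×0.9 − 0.9×0.5 = 0.36. vA = 0.9 + 0.09×0.81 = 0.973 and vV = 0.9 + 0.09×0.25 = 0.9225, so SE = 0.138 and power is 74%.

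Post-baseline only: the expected difference stays at 0.40 and SE = √(1/nA + 1/nV). At 10% in both arms, √(2/90) = 0.149 and power is 76%.

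| Dropout, active / vehicle | Baseline carried: difference (SD) | Power | Post-baseline only: difference (SD) | Power |
|---|---|---|---|---|
| 0 / 0 | 0.40 | 80% | 0.40 | 80% |
| 10% / 10% | 0.36 | 74% | 0.40 | 76% |
| 15% / 5% | 0.29 | 55% | 0.40 | 76% |
| 20% / 5% | 0.245 | 43% | 0.40 | 75% |
| 5% / 15% | 0.43 | 88% | 0.40 | 76% |

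**4. No drug effect**

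With δ = 0, 20% versus 5% dropout and Visit 2 carried: 0.80×0.5 − 0.95×0.5 = −0.075 SD, a false difference against active. Two-sided rejection rises from 5% to about 8 to 9%. Under the post-baseline-only reading and the same assumptions there is no false difference.

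**The case against.** The strongest reply is that the governing rule cannot be seen. SAP 8.2 takes precedence and its text is withheld, as are the baseline definition and the efficacy methods. It may already restrict LOCF to post-baseline values or exempt CAE endpoints. The table titles are also cut, so none can be shown to apply LOCF to a CAE endpoint. Observed-data tables are listed throughout, Protocol 7.1.2 limits post-CAE endpoints to where they are available, and the SAP calls all endpoints hypothesis-generating. This stands as a limit on confidence and weight. It does not alter the schedule: no wording in SAP 8.2 can supply an on-treatment CAE value that was never collected. The phrase about availability covers visits without a CAE but gives no rule for a subject missing at Visit 6.

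Three stronger readings are tempting and are not supported:

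- *That early leavers cannot be scored at all.* A literal LOCF does score them, as zero change. What is missing is a score from an on-treatment value.
- *That LOCF would fill the two parts of a pre- to post-CAE change from different visits*, setting an untreated post-CAE score against a treated pre-CAE score. Nothing in the documents proposes this. It is worth ruling out in words, but it is not a planned analysis.
- *That 55% power, or a Phase 3 inflated by (0.40/0.29)² = 1.9, is the expected cost.* Those figures need Visit 2 to be carried and dropout to be unequal. With 10% in both arms the ratio is (0.40/0.36)² = 1.23. Under the post-baseline-only reading with dropout unrelated to outcome, the expected effect is unchanged.

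**Conclusion.** The point holds in limited form. For anyone who leaves before Visit 6, the visible ITT/LOCF rule has no on-treatment post-CAE, during-CAE or pre- to post-CAE value to use. Pre-CAE and non-CAE endpoints are unaffected in subjects measured at Visit 3, 4 or 5.

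The cost depends on a choice that the visible text does not make. If Visit 2 is carried, the loss is modest under equal dropout (80% to 74% power at 10%) and serious under unequal dropout (55% at 15% versus 5%). If it is not carried, the loss is small (80% to 76% at 10%), but the result is a completers' comparison and is unbiased only if dropout is unrelated to outcome. All of these sizes rest on assumed dropout, vehicle response and effect.

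The change is worth making in this Phase 2b trial because it is meant to inform Phase 3 endpoint choice and sample size, and because one endpoint at week 12 suffices for success. Confidence is medium, since SAP 8.2 may already settle which reading applies. The visible table list nonetheless offers only LOCF and observed-data analyses, and neither handles the missing Visit 6 value well.

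**What to change.** 1. State in Protocol 11.4.3 and SAP 8.2, or confirm if it is already there, that Visit 2 CAE values are never carried to week 12, and that a pre- to post-CAE change uses two values from the same visit.
2. For post-CAE, during-CAE and pre- to post-CAE endpoints, replace LOCF with an analysis of all randomised subjects. Multiply impute the missing Visit 6 value by arm, using the Visit 2 pre- and post-CAE scores and the week 2, 4 and 8 non-CAE scores where collected.
3. Keep the planned observed-data tables as supporting analysis. A vehicle-based imputation is an optional sensitivity analysis.

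Cost: wording in two documents and some imputation code, with no new visit, procedure or subject. The downsides are a different missing-data method for CAE endpoints than for the others, and reliance on a missing-at-random assumption. No on-treatment CAE score before Visit 6 exists to inform the imputation, so it depends on the non-CAE scores and the Visit 2 CAE scores being predictive. If SAP 8.2 already bars carrying Visit 2, step 1 is only a confirmation and step 2 remains the improvement.

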### 6 STUDY POPULATION

# 6.1 Number of Subjects (approximate)

It is estimated that approximately 750 subjects will be screened to enroll approximately 300 randomized subjects (100 in each group). Subjects will be randomized in a 1:1:1 ratio of Reproxalap Ophthalmic Solution (0.1%) to Reproxalap Ophthalmic Solution (0.25%) to vehicle ophthalmic solution.

## 6.2 Study Population Characteristics

All subjects must be at least 18 years of age, of either gender, and of any race, and must meet all inclusion criteria and none of the exclusion criteria.

### 6.3 Inclusion Criteria

### Each subject must:

- 1. Be at least 18 years of age of either gender and any race;
- 2. Provide written informed consent and sign the Health Information Portability and Accountability Act (HIPAA) form;
- 3. Have a reported history of dry eye for at least 6 months prior to Visit 1;
- 4. Have a history of use or desire to use eye drops for dry eye symptoms within 6 months of Visit 1;
- Report a score of 6. Have a Schirmer's Test score of Visit 1 and Visit 2; Have a tear at Visit 1 and Visit 2 Have a corneal fluorescein staining score at Visit 1 and Visit 2 9. Have a sum corneal fluorescein staining score , at Visit 1 and Visit 2 10. Have a total lissamine green conjunctival at Visit 1 and Visit 2 at Visits 1 and 2 as defined by: 11. Demonstrate a response to the fluorescein staining in the A. Having at least inferior region in at least one eye following exposure; Reporting an Ocular Discomfort 2 or more consecutive B. time points in at least one eye during

### 6.4 Exclusion Criteria

### Each subject may not:

- 1. Have any clinically significant slit lamp findings at Visit 1 that may include active blepharitis, meibomian gland dysfunction (MGD), lid margin inflammation, or active ocular allergies that require therapeutic treatment, and/or in the opinion of the investigator may interfere with study parameters;
- 2. Be diagnosed with an ongoing ocular infection (bacterial, viral, or fungal), or active ocular inflammation at Visit 1;
- 3. Have worn contact lenses within 7 days of Visit 1 or anticipate using contact lenses during the study;
- 4. Have used any eye drops within 2 hours of Visit 1;
- 5. Have previously had laser-assisted in situ keratomileusis (LASIK) surgery within the last 12 months;
- 6. Have used cyclosporine 0.05% or lifitigrast 5.0% ophthalmic solution within 90 days of Visit 1;
- 7. Have any planned ocular and/or lid surgeries over the study period or any ocular surgery within 6 months of Visit 1;
- 8. Be using or anticipate using temporary punctal plugs during the study that have not been stable within 30 days of Visit 1;
- 9. Be currently taking any topical ophthalmic prescription (including medications for glaucoma) or over-the-counter (OTC) solutions, artificial tears, gels or scrubs, and cannot discontinue these medications for the duration of the trial (excluding medications allowed for the conduct of the study);
- 10. Have corrected visual acuity greater than or equal to logarithm of the minimum angle of resolution (logMAR) + 0.7 as assessed by Early Treatment of Diabetic Retinopathy Study (ETDRS) scale in both eyes at Visit 1;
- 11. Be a woman who is pregnant, nursing, or planning a pregnancy;
- 12. Be unwilling to submit a urine pregnancy test at Visit 1 and Visit 6 (or early termination visit) if of childbearing potential. Non-childbearing potential is defined as a woman who is permanently sterilized (e.g., has had a hysterectomy or tubal ligation), or is post-menopausal (without menses for 12 consecutive months);
- 13. Be a man or woman of childbearing potential who is not using an acceptable means of birth control; acceptable methods of contraception include: hormonal oral, implantable, injectable, or transdermal contraceptives; mechanical spermicide in conjunction with a barrier such as a diaphragm or condom; intrauterine device (IUD); or surgical sterilization of partner. For non-sexually active males or females, abstinence may be regarded as an adequate method of birth control; however, if the subject becomes sexually active during the study, he/she must agree to use adequate birth control as defined above for the remainder of the study;
- 14. Have a known allergy and/or sensitivity to the test article or its components;
- 15. Have a condition or be in a situation which the investigator feels may put the subject at significant risk, may confound the study results, or may interfere significantly with the subject's participation in the study;
- 16. Be currently enrolled in an investigational drug or device study or have used an investigational drug or device within 30 days of Visit 1;

- 17. Have previously used reproxalap ophthalmic solution;
- 18. Be currently using any medication known to cause ocular drying that is not used on a stable dosing regimen for at least 30 days prior to Visit 1;
- 19. Be unable or unwilling to follow instructions, including participation in all study assessments and visits.

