### 9.1.5 Methods for Assignment to Treatment Groups:

Before the initiation of study run-in at Visit 1, each subject who provides written and informed consent will be assigned to a screening number. All screening numbers will be assingned in strict numerical sequence at a site and no numbers will skipped or omitted. Each subject who meets all the inclusion and none of the exclusion criteria at Visit 1 and Visit 2 will be assigned a randomization number at the end of Visit 2. The Interactive Web Response System (IWRS) will be used to assign all randomization numbers.

Randomization and kit numbers will be assigned automatically to each subject as they are entered into the IWRS.

The site staff will dispense kit(s) required until the next visit. Both the randomization number and the dispensed study drug kit number(s) will be recorded on the subject's

source document and eCRF. The sponsor, investigators, and study staff will be masked during the randomization process and throughout the study.

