### 9.3.2 Visit 1: Day $-14 \pm 2 - CAE^{\circ}$ Screening

All subjects will undergo the following screening assessments:

- Demographic Data and Medical/Medication/Ocular History
- Review of Inclusion/Exclusion Criteria
- Urine Pregnancy Test (for females of childbearing potential): Women of childbearing potential must have a negative urine pregnancy test to continue in the study

Post−CAE®

- AE Query
- IOP
- Dilated Fundoscopy
- Review of Inclusion/Exclusion Criteria
- Run-in Instillation at the Study Site: All subjects having a positive response (as
  defined above) and meeting all other screening eligibility criteria at the end of Visit 1
  will receive run-in drops for dosing. Qualified subjects will self-administer their
  initial run-in dose bilaterally at the study site under supervision of a trained
  technician.
- Run-in (Vehicle) and Diary Dispensation: Prior to discharge from the study site on
  Day -14, subjects will be dispensed sufficient Run-in supply to last until Visit 2 and
  will be educated in diary recording and self-administration of vehicle run-in. Subjects
  will be instructed to self-administer one drop QID in each eye until Visit 2. Subjects
  will be instructed NOT to instill run-in on the morning of their next scheduled study
  visit (Visit 2).

- AE Query
- Subjects will be scheduled for Visit 2.

- Diary/Run-in Collection
- Review of Inclusion/Exclusion Criteria
- Medical/medication history update
- AE query

[figure not shown]

- Review of Inclusion/Exclusion Criteria
- Randomization
- Study Drug Instillation at the Study Site: All subjects having a positive response (as
  defined above) and meeting all other screening eligibility criteria at the end of Visit 2
  will be randomized to one of three treatment groups utilizing the IWRS system.
  Randomized subjects will self-administer their initial study drug dose bilaterally at
  the study site under supervision of a trained technician.
- Study Drug Diary/Study Drug Dispensation: Prior to discharge from the study site on Visit 2 (Day 1), randomized subjects will be educated in study drug diary recording and self-administration of study drug. Subjects will receive their assigned study drug kit with sufficient supply to last until Visit 3 and will be instructed NOT to selfadminister study drug on the morning of their next scheduled study visit (Visit 3).
- AE Query
- Subjects will be scheduled for Visit 3.

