### 9.3.7 Visit 6: Day $85 \pm 3$

[figure not shown]

- Drug Diary/Study Drug Collection
- · Medical/medication history update
- AE query
- Urine Pregnancy Test (for females of childbearing potential)
- · \_\_\_\_\_

- .
- Utilizing an ETDRS Chart

- Intraocular Pressure
- Dilated fundoscopy
- AE Query
- Study Exit

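### No pregnancy test is stated at Visit 2, where the first study drug dose is given 12 to 16 days after the only stated pre-treatment test

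*Protocol*

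**What the plan says.** - **Who is excluded.** Protocol section 6.4, item 11, bars anyone who would "Be a woman who is pregnant, nursing, or planning a pregnancy". No visit is attached to this item.
- **When a test is named.** Item 12 excludes a subject who would "Be unwilling to submit a urine pregnancy test at Visit 1 and Visit 6 (or early termination visit) if of childbearing potential". The synopsis carries the same rule.
- **What the Visit 1 test decides.** Section 9.3.2 states: "Women of childbearing potential must have a negative urine pregnancy test to continue in the study". What follows Visit 1 is a vehicle run-in.
- **When eligibility must hold.** Section 9.1.5 states: "Each subject who meets all the inclusion and none of the exclusion criteria at Visit 1 and Visit 2 will be assigned a randomization number". SAP section 4.1 repeats this.
- **When study drug starts.** The Visit 2 procedures state: "Randomized subjects will self-administer their initial study drug dose bilaterally at" the study site, after randomisation.
- **What else is done at Visit 2.** The surviving items include "Review of Inclusion/Exclusion Criteria" twice, the second time directly before randomisation, and an update of medical and medication history. No pregnancy test is visible among them.
- **Later tests.** The test reappears in section 9.3.7 (Visit 6, Day 85 ± 3). Section 9.4.2 lists it as optional at an unscheduled visit.
- **Contraception.** Item 13 excludes subjects of childbearing potential who do not use an acceptable method.

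**The concern.** The single stated pre-treatment test sits before the vehicle run-in and not before the investigational drug. Two of the three arms start reproxalap at Visit 2. A woman who conceived too shortly before Visit 1 to test positive, or who conceived during the run-in and does not yet know it, passes every stated check and can be randomised. The next scheduled test is at Visit 6 or early termination. At stake is exposure of an early pregnancy to an investigational drug for up to about 12 weeks, in a group that the protocol itself chose to exclude. The efficacy analysis is not affected.

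**Working it through.** **1. The plan's own interval.** The synopsis gives a run-in of 14 ± 2 days. SAP section 3.1 says that there is no Day 0 and that Day 1 is the day of randomisation. So:

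gap = 1 − (Visit 1 day) − 1

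- Visit 1 on Day −16: 1 + 16 − 1 = 16 days
- Visit 1 on Day −14: 1 + 14 − 1 = 14 days
- Visit 1 on Day −12: 1 + 12 − 1 = 12 days

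This reproduces 14 ± 2. Counting a Day 0 would give 13 to 17, which does not match.

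**2. Interval between stated tests.** Visit 1 to Visit 6 is 98 days nominally (84 + 14, as in protocol section 9.8), with a range of 93 (Day −12 to Day 82) to 103 (Day −16 to Day 88). Visit 2 to Visit 6 is 84 days, range 81 to 87.

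**3. Expected number of undetected pregnancies at first dose.** The documents give none of the following inputs; they are assumptions:

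- 30 to 90 of the 300 randomised subjects are of childbearing potential;
- the conception risk on contraception is 0.2 to 1% per month (30.4 days);
- a urine test turns positive about 14 days after conception.

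Under the present plan the undetected window is the 14 days before Visit 1, too recent to show at that test, plus the nominal 14-day run-in: 28 days.

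- Low: 30 × 0.002 × 28/30.4 = 0.055
- High: 90 × 0.01 × 28/30.4 = 0.83

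Only two thirds of subjects receive reproxalap (1:1:1):

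- Low: 0.055 × 2/3 = 0.04
- High: 0.83 × 2/3 = 0.55

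**4. What a Visit 2 test would avert.** On the same latency, a test on Day 1 detects conceptions more than about 14 days old, that is, from before about Visit 1. That is 14 of the 28 days, or half. At the window limits it is 12 of 26 days (46%) or 16 of 30 days (53%). On active drug:

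- Low: 0.037 × 0.5 = 0.02
- High: 0.55 × 0.5 = 0.28

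Almost all of the gain comes from conceptions shortly before Visit 1. Most conceptions during the run-in would still test negative.

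**The case against.** Four arguments carry weight.

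**The documents do not contradict themselves.** A reader might infer that the pregnancy exclusion cannot be enforced at randomisation, or that item 12 conflicts with section 9.1.5. Neither is supported. Section 9.1.5 requires the criteria to be met at both visits; it does not require each to be measured afresh at Visit 2. Exclusion items 1, 2 and 10 (slit-lamp findings, infection or inflammation, visual acuity) are tied to Visit 1 only. The Visit 2 criteria review and history update allow a known or suspected pregnancy to be excluded, and item 13 lowers the risk in the interval. This stands. What remains is that these safeguards rest on report and cannot find an unrecognised early pregnancy.

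**A Visit 2 test may exist in text that is not shown.** The Visit 2 procedure list is fragmentary, and neither protocol Appendix 1 nor the schedule in SAP section 3.2 can be read. A test there cannot be ruled out, so it would be wrong to state as fact that Visit 1 has the only pre-dose test. It does look unlikely: item 12 is intact in two places, and the pregnancy-test line is legible at Visit 1, Visit 6 and unscheduled visits. If the hidden schedule does contain a Visit 2 test, item 12 still omits it.

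**The benefit is small and partial.** On the assumptions above, a Visit 2 test averts well under one exposure in the whole trial and misses most run-in conceptions. This stands and sets the weight of the point.

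**The consequence cannot be judged from these documents.** They show no reproductive-risk information and refer to the Investigator's Brochure for risks. This also stands.

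**Conclusion.** The point holds as a cheap improvement. It is neither an internal contradiction nor a flaw in the trial's inference. On the legible text, the stated pre-treatment pregnancy test precedes the first study drug dose by 12 to 16 days, and no stated test verifies non-pregnancy at randomisation. The interval follows from the documents alone. The expected counts (0.04 to 0.55 undetected pregnancies starting active drug, about half of them avertable) rest entirely on the assumed number of subjects of childbearing potential, the conception rate and the test latency, and should be read as orders of magnitude. The conclusion that no Visit 2 test is planned remains subject to the unredacted schedule.

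**What to change.** 1. Check the unredacted Visit 2 procedure list, protocol Appendix 1 and the SAP section 3.2 schedule for a Visit 2 pregnancy test.
2. If there is one, correct item 12 in section 6.4 and the synopsis so that it names Visit 2.
3. If there is none, reconcile items 11 and 12 with section 9.1.5: add Visit 2, before randomisation, to the visits named in item 12 (both places), to the Visit 2 procedure list and to the schedules.
4. Keep the Visit 1 test. Moving it to Visit 2 would remove the gate that section 9.3.2 sets before run-in dosing.

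The cost is one extra urine dipstick for each woman of childbearing potential who reaches Visit 2, at a visit that already takes place, plus a wording change. The gap from last stated test to first dose falls from 12 to 16 days to zero, and the longest interval between stated tests falls from 93–103 days to 81–87 days.
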